12.1 Inclusion criteria

- 1 Clinicians working in an adult palliative care service.
- 2 Willing and able to provide written informed consent.

12.2 Exclusion criteria

Participants who do not meet the inclusion criteria will be excluded

12.3 Recruitment

In both study arms, before participants complete the vignettes, they will be asked to complete a brief demographic section. Questions in this section will be used to assess the participant's eligibility for the study (i.e. are they a clinician working in palliative care for adults) as well as to describe the study population and conduct analyses of associations between judges' characteristics and their integration of advice.

12.3.1 Arm A (*recruited at (online) seminars*)

Clinicians will be recruited at (online) seminars where the CI is scheduled to give presentations on prognostication. The study will be presented before the seminar and attendees will be invited to fill

in the online questionnaire in preparation for the seminar. The CI will stress that participation in the study is voluntary. The study can be completed by international clinicians attending the (online) seminars.

12.3.2 Arm B (*recruited online*)

We will recruit clinicians to complete the online survey in the time period from August 2020 to April 2021, and we will identify eligible clinicians in several ways. The Hospice UK website includes a database listing adult and children's hospice care providers in the UK (<https://www.hospiceuk.org/about-hospice-care/find-a-hospice>). The database includes 310 hospices, of which 47 hospices have the word 'children' in their name. We will start by approaching a small number of the remaining 263 hospices on the list to explore the ease of recruitment for this study. We will not recruit from NHS services. In a first wave of recruitment, we will approach the nine Marie Curie hospices in the UK (Belfast, Bradford, Cardiff and the Vale, Edinburgh, Glasgow, Hampstead, Liverpool, Newcastle, and West Midlands), as these hospices may be more inclined to participate because of their link with Marie Curie. We will approach additional hospices as needed until we reach our lower limit for our sample size (see more in section 16.1 Sample size calculation). We will make individual contact with each hospice to inform them about the study, which could include approaching the medical director, head of nursing or matron, and/or the education and research lead. We will initially approach hospices via email and then follow up with a phone call, we will offer that the research team should come and present the study at their unit. If the hospice agrees to participate in the study, we will forward the template for the invitation email to be circulated to all doctors and nurses working in the hospice.

If necessary, we will use additional recruitment strategies, including Marie Curie Palliative Care Research Department's social media platform or newsletters, where interested clinicians will be able to contact the research team to participate in the study.

12.4 Informed consent

Participants will consent to complete the decision tasks, to have their data collected, stored and processed, to receive a results summary, and to be contacted by the research team to be prompted to complete the study.

Participants will receive information about the aims, methods, anticipated benefits and potential hazards of the study in the invitation email, on the study website and in the PIS. The PIS will be available to download from the study website. This information includes an explanation that participants are under no obligation to enter the study and that they can withdraw at any time during the study, without having to give a reason. It also includes a transparency message to inform participants how we will use their information.

On completion, a debrief page will be provided to remind the participant what the results will be used for. Contact details will be provided on the introduction and debrief pages should participants have any questions or issues they wish to follow up.

Informed consent will be obtained via checkboxes before starting the study assessments. The checkboxes will be to confirm that the participant is willing:

- 1 To participate.
- 2 To acknowledge the results will be used in future publications and research.
- 3 To provide an email address in order to enable participants to log out and return, and for the research team to send reminder emails, send feedback and approach them about future research, if desired.

12.5 Participant withdrawal

A participant may be withdrawn from the study whenever continued participation is no longer in the participant's best interests, but the reasons for doing so must be recorded. Reasons for discontinuing the study may include:

- 1 Participants withdrawing consent
- 2 Persistent non-compliance to protocol requirements

The decision to withdraw a participant from the study will be recorded in the study database. If a participant explicitly states they do not wish to contribute further data to the study their decision will be respected and recorded in the study database.

Throughout the study, the research team will monitor and review the responses given by the participants, and the time taken by each participant to complete the online decision tasks; in order to assess for compliance with the protocol. Participants may be excluded from the analysis if their response record strongly suggests that they did not comply with the study protocol (e.g. all vignettes answered too speedily or with the same response).

13 Recording and reporting of adverse events

This is a very low risk study. Clinicians will be asked to review ~~either one or~~ five vignettes and will receive advice from an advisor. Clinicians will be familiar with the type of information provided. Clear instructions and appropriate debrief will be provided. For these reasons, there are no expected adverse events of our study.

13.1 Notification of reportable protocol violations

A reportable protocol violation is a breach which is likely to effect to a significant degree:

- (a) the safety or physical or mental integrity of the participants of the study; or
- (b) the scientific value of the study.

The sponsor will be notified immediately of any case where the above definition applies during the study conduct phase.

14 Data management

14.1 Confidentiality

All data will be handled in accordance with the General Data Protection Regulation. Participants will be asked for their email address as well as being assigned a participant ID. The purpose of this is to:

- Enable the participant to log out and back in to the study website to continue the series of vignettes
- Contact participants with a reminder email if the participant should not complete the series of vignettes. One reminder email will be sent, one week after starting the study/the last website visit (Arm B only)
- Populate the certificate of participation at the end of the study
- Send feedback at the end of the study
- Contact participants regarding future studies

The participants will not be asked for any other personal identifiable information.

15 Data handling

In the study, demographic data and estimates of probabilities obtained through decision tasks will be collected from professionals in accordance with the PIS and participants' informed consent.

Data obtained from the study will be kept on a web-based database on UCL servers, which is encrypted and password protected. The database will be accessible only to approved members of the research team by limiting access to the intranet to their IP addresses. Once online data collection is completed, the research team at Marie Curie Palliative Care Research Department will download the data from the website for statistical analysis at UCL. UCL will act as the data controller.

This database will be pseudonymised as only the participant ID will be referenced, but a separate database linking email addresses with participant ID numbers (but not with other study data) will be kept in a separate location on UCL servers. Email addresses will be encrypted in the database with the decryption key stored in a separate location. The only member of the study team who will have access to this database is [name]. These data will only be used if requested by relevant authorities, such as to demonstrate the authenticity of the data. The copy of the final databases including email addresses will be retained until three years after publication of the last paper arising from the study, or no longer than five years from the end of data collection.

A separate database of email addresses will be kept for those participants who have indicated that they are willing to be approached for future research.

A UCL email account will be set up for members of the study team to contact participants. Emails held in this account will include participants' email addresses but not their participant ID. These data will be retained until three years after publication of the last paper arising from the study, or no longer than five years from the end of data collection.

Procedures for data handling will be explained clearly in the PIS and informed consent will be sought.

The research team at Marie Curie Palliative Care Research Department will process, store and dispose of all data in accordance with all applicable legal and regulatory requirements, including the Data Protection Act 1998, the GDPR, and any amendments thereto. Data will be stored on password protected, access-restricted, shared drives (S:Drive) on UCL servers. The S:Drives are maintained by UCL and routinely backed up.

Data (suitably anonymised) may be shared with other research groups if a reasonable request is submitted to and agreed by the CI.

16 Statistical Considerations

16.1 Sample size calculation

We aim at recruiting between 100-200 clinicians within the 10 month time period of recruitment (August 2020-April 2021). This will be sufficient to address the objectives of the study. We will stop recruiting and close down the website when we have accrued 300 respondents with complete data within the recruitment period (before April 2021).

We want to compare the means of the weighting of advice (WOA) of the two groups, (the group receiving advice labelled as coming from an algorithm and the group receiving advice labelled as coming from a clinician), with a confidence interval (CI) of 95%. Based on calculations from a similar study by Logg et al. (2019) we expect the standard deviation (SD) to be between 0.3 and 0.4. This will give a width of the CI between 0.17 and 0.31, depending on the sample size and the SD (see the table below). These numbers are based on and calculated from the guidelines by Machin et al. (2018). This means that a sample size between 100-200 respondents should be sufficient to detect a significant difference between the mean WOAs of the two groups if the mean difference is greater than 0.085 to 0.22.

Table 1: The width of the confidence interval varying by sample size and SDs

Sample Size	Expected SD for mean diff in WOA	
	$\sigma = 0.3$	$\sigma = 0.4$
50	0.33	0.44
100	0.24	0.31
150	0.19	0.26
200	0.17	0.22
250	0.15	0.20
300	0.14	0.18

The calculations above are sufficient to address the primary objective of the study which is to assess the level to which clinicians incorporate advice received from other clinicians or an algorithm into their estimates of the prognosis of palliative care patients.

The online survey consists of five vignettes. Increasing the number of vignettes would increase generalisability of the study but would add to the study burden for the participants and increase the risk that the study would not be completed by respondents. It was considered that five vignettes was a suitable balance between generalisability and study burden.

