Study design and methods:	In this study, using the Judge-Advisor System, we will recruit clinicians working in palliative care for adults. Participants will be asked to complete a survey and review five patient summaries ("vignettes") based on real cases derived from a previous study. Clinicians will be presented with key prognostic information and will be asked to provide an estimate of the probability that the patient will survive for two weeks (0-100%). After providing this initial estimate, participants will receive prognostic advice. While in reality all participants will receive the same advice, participants will be randomised into two groups and these groups will be informed that the advice is either: (1) provided by an algorithm; or (2) provided by a team colleague. Participants will then be given the opportunity to give a second, possibly revised estimate in the light of the advice received.
	Study data will be collected using two different recruitment methods (Arm A and Arm B). Participants in arm A will be recruited at a series of (online) seminars, and participants in arm B will be recruited through their hospice employment. All participants will be asked to complete an online questionnaire, including five vignettes. Clinicians will be asked some demographic questions including age, gender, profession and experience.
Study duration per participant:	Approximately 10-15 minutes
Estimated total study duration:	36 months
Planned study sites:	For arm A, we will approach clinicians attending a series of (online) seminars on palliative care. For Arm B, we will approach clinicians working in non-NHS hospices in the UK.
Total number of participants planned:	100-300
Main inclusion/exclusion criteria:	Participants must be clinicians working in palliative care for adults. They must be willing and able to provide informed consent

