Clinicians will be invited to participate in the study as part of a (online) seminar on palliative care by the CI or through an invitation email sent to their hospice medical director (see section 12.3). Seminar participants will receive information about the study before the seminar and will be invited to complete the online questionnaire in preparation for the seminar. The CI will make it clear that delegates at the seminar are under no obligation to complete the questionnaire.

Participants will be provided with a link to the study website and will complete all assessments online. The website will provide information regarding the study and a link to a PIS. Participants will be asked to tick check boxes to indicate that they are giving informed consent. After filling in the demographics section, eligible participants will be considered to be enrolled and a participant ID will be assigned. Next, participants will be randomly allocated to one of the two study groups. This will be performed through the web-based system, using a pre-generated blocked randomisation list.

Participants will be given tailored instructions, shown a practice vignette and will then be able to start the decision tasks and to provide estimates of the probability of patients surviving two weeks. Participants will be presented with five vignettes. Vignettes will be presented in random order to prevent order effects.

There will be no time limit for completion, so that each participant will be able to consider their responses. Participants will be given the opportunity to log out and return to the same place at a more convenient time. Participants will not be able to move on to the next page if required information is missing or is in an incorrect format (e.g. incorrect email format). The online environment will be piloted by the study team in close collaboration with the study statistician who will review the data being collected before, during, and at the start of the recruitment phase to ensure data integrity.

After completing the series of vignettes, participants will be shown a debrief page to remind the participant what the results will be used for and they will be able to download a certificate of participation. Participants will be asked if they wish to receive a summary of the results at the end of the study and whether they would be willing to be approached for subsequent studies.

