4.2 Missing data

Participants who do not complete the five vignettes will be removed from the analysis.

We will report the number of vignettes each participant completed. Potential bias due to missing data will be investigated by comparing characteristics of those who completed sufficient vignettes with those who did not complete sufficient vignettes.

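### The 95% CI widths of 0.17-0.31 hold for 100-200 clinicians analysed, but the target and the lower limit of 100 are not defined as completers, so the upper width of 0.31 is not secured

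*Protocol*

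**What the plan says.** **Target.** Protocol 16.1: "We aim at recruiting between 100-200 clinicians within the 10 month time period of recruitment (August 2020-April 2021". The same section gives a CI width of 0.17 to 0.31 for SDs of 0.3 to 0.4, read from Table 1 at 100 and 200. The Summary (section 6) and SAP section 1 give the planned total as 100-300.

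**Ceiling.** Protocol 16.1 closes the website "when we have accrued 300 respondents with complete data within the recruitment period".

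**Lower limit.** Protocol 12.3.2 (Arm B): "We will approach additional hospices as needed until we reach our lower limit for our sample size", with a pointer to 16.1. The only figure there that can serve as a lower limit is 100. Neither section says whether it counts people enrolled or people with complete data.

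**Enrolment.** Protocol section 11: once the demographic questions are answered, "eligible participants will be considered to be enrolled and a participant ID will be assigned". Randomisation follows, and then the vignettes.

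**Removal.** SAP 4.2: "Participants who do not complete the five vignettes will be removed from the analysis". Protocol 16.2 says the same and also removes protocol violators, as does SAP 2.2. Protocol 12.5 allows exclusion of those who answer implausibly fast.

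**Loss.** Neither document states a completion rate or an inflation of the target.

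**The concern.** The precision statement and the recruitment target use different units. A width calculated for N analysed is attached to N recruited, and the plan contains a step that makes the second number larger than the first. The ceiling shows that the authors had the right unit available but did not apply it to the lower end.

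The lower limit has a practical role: it tells the team when it need not approach further hospices. Someone who reads it as 100 enrolled could end that outreach and then analyse fewer than 100. The interval for the algorithm-versus-clinician comparison would be wider than 16.1 states, and the assurance that 100-200 is enough would rest on an analysed number that the plan does not secure.

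**Working it through.** **Inputs.** The 95% confidence level, SDs of 0.3 and 0.4, and totals of 100 and 200 come from protocol 16.1. Equal allocation is assumed because the ratio is not stated. Loss is assumed at 10, 20 and 30%, equal in both groups.

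**Step 1: reproduce Table 1.** With N analysed in total and N/2 per group:

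width = 2 × 1.96 × SD × √(4/N)

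This is 2.352/√N at SD 0.3 and 3.136/√N at SD 0.4.

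- N = 100: 0.235 and 0.314 (Table 1: 0.24 and 0.31)
- N = 200: 0.166 and 0.222 (Table 1: 0.17 and 0.22)
- N = 300: 0.136 and 0.181 (Table 1: 0.14 and 0.18)

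All 12 cells agree to two decimals. Reading N as the number per group gives 0.166 and 0.222 at 100, which does not fit. The table is therefore correct, takes N as the total analysed, and contains no loss factor.

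**Step 2: apply an assumed loss d.** Replace N by N(1 − d).

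| Recruited | Loss | Analysed | Width, SD 0.3 | Width, SD 0.4 |
|---|---|---|---|---|
| 100 | 0% | 100 | 0.235 | 0.314 |
| 100 | 10% | 90 | 0.248 | 0.331 |
| 100 | 20% | 80 | 0.263 | 0.351 |
| 100 | 30% | 70 | 0.281 | 0.375 |
| 200 | 10% | 180 | 0.175 | 0.234 |
| 200 | 20% | 160 | 0.186 | 0.248 |
| 200 | 30% | 140 | 0.199 | 0.265 |

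Only the cells with 100 recruited and SD 0.4 exceed 0.31. At SD 0.3, even a 40% loss from 100 gives 2.352/√60 = 0.304. At 200 recruited and SD 0.4, it takes a 50% loss to reach 0.314.

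**Step 3: slack at the lower end.** For the width to round to 0.31 at SD 0.4, N must be at least 4 × (2 × 1.96 × 0.4/0.315)² = 99.1, that is 100 analysed. There is no room for loss at that point.

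**Step 4: recruits needed, N/(1 − d).** For 100 analysed: 112, 125 and 143 at 10, 20 and 30% loss. For 200 analysed: 223, 250 and 286. All are below 300.

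**The case against.** A reader might infer that the design cannot deliver its stated precision, or that Table 1 is wrong. The documents support neither.

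- **The ceiling.** Recruitment closes at 300 respondents with complete data or at the end of the period. At 300 the widths are 0.14 and 0.18. The lower limit governs only approaches to additional hospices in Arm B. It does not close the website, halt the Arm A seminars or stop hospices already approached. This stands, and it makes the shortfall conditional. But a ceiling permits accrual beyond 100; it does not require it.
- **The unit.** Section 16.1 also speaks of a sample of 100-200 respondents, which could mean completers. That is possible, so the unit is undefined rather than shown to be recruits. Against that reading, the section adds a complete-data qualifier to respondents when it sets the ceiling, and elsewhere writes of respondents who do not finish.
- **Expected loss.** The phrase "increase the risk that the study would not be completed by respondents" concerns adding more vignettes and is not a forecast of loss at five. This stands. The removal rules, the Arm B reminder (protocol 14.1) and the planned comparison of completers with non-completers (SAP 4.2) nevertheless show that some loss is provided for.
- **Repeated vignettes.** Table 1 uses one value per participant, while SAP 4.3 models five. If 0.3-0.4 is a per-vignette SD, averaging multiplies the variance by (1 + 4 × ICC)/5. That is 0.84 at an ICC of 0.8 and 0.68 at 0.6, which would offset about 16% or 32% loss. Neither the level of the SD nor an ICC is stated, and Table 1 takes no such credit, so this offset cannot be relied on.
- **Monitoring.** Responses and recruitment figures are reviewed during the study (protocol 12.5 and 18), so the team may well notice non-completion. No rule makes them act on it.

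**Conclusion.** The point holds as a mismatch of units at the lower end of the target. The widths of 0.17-0.31 are correct for 100-200 analysed, but the plan words the target as recruitment, leaves the unit of the lower limit open, removes non-completers and violators, and allows for no loss. The upper width of 0.31 is therefore not secured.

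The effect is modest and depends on three things together: accrual ending near 100, that figure counting recruits, and an SD near 0.4. The width is then about 0.33, 0.35 or 0.37 at 10, 20 or 30% loss. With 200 recruited, the same losses give 0.175-0.265, inside the stated range. The loss rates are assumptions, and the calculation assumes equal groups and one value per participant, as Table 1 does.

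**What to change.** In protocol 16.1 and 12.3.2, define the lower limit of 100 and the 100-200 target as analysable participants with complete data, the unit already used for 300. Label N in Table 1 as the number analysed. The range 0.17-0.31 then needs no change.

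Only if the target stays in recruits, restate the width for an explicitly assumed analysable fraction instead. At 80%, for example, 100-200 recruited means 80-160 analysed and a width of 0.19 (SD 0.3, 160 analysed) to 0.35 (SD 0.4, 80 analysed). The two changes are alternatives and should not be combined.

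**Cost.** The first option takes a few words in two sections and a table label. Hospice outreach may run somewhat longer: 112 to 143 recruits for 100 analysed at 10-30% loss. The second option makes the stated precision slightly less favourable. The SAP is dated 26 March 2021 and recruitment was planned to end by April 2021, so at that stage the change would serve mainly to make the reported precision match the set analysed.

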7.5 JAS research in the context of this study

While research is available on advice and information seeking among clinicians (Rappolt, 2002, Weber et al., 2007, Weinberg et al., 1981) to the best of our knowledge no experimental studies have used the JAS to explore the dynamics of receiving and using advice in the context of medical prognostic decision-making.

In the context of our study, it is often the responsibility of a (senior) doctor to formulate a prognosis to consider hospice enrolment, assess eligibility for a clinical study, plan care and treatment, and prepare patients and families. As described above, doctors could obtain advice in a formal MDT setting or ask a more experienced colleague, a colleague from a different background that brings a different perspective, or a colleague who has spent more time with the patient. JAS studies have used different types of questions, including estimations of the dates of historical events and multiple-choice questions (Bonaccio and Dalal, 2006). The current study will ask participants to estimate the probability of patients surviving two weeks (0-100%).

A recent series of experiments using a variety of judgement tasks has shown that, contrary to prior work, people placed a higher weight on advice from an algorithm as compared to advice from another person (Logg et al., 2019). The researchers provided judges in the study with equivalent advice that was labelled as coming from an algorithmic versus human source. In the first experiment, judges were asked to estimate the weight of a person in a photograph. The actual weight of this person was 164 pounds. All judges then received the same advice (163 pounds), which was the estimate provided by 415 participants in another experiment (Moore and Klein, 2008). Half of the judges were told that: 'An algorithm ran calculations based on estimates of participants from a past study. The output that the algorithm computed as an estimate was: 163 pounds'. The remaining judges were told that 'The average estimate of participants from a past experiment was: 163 pounds'. In this study, we will do an experiment similar to this, by randomising clinicians to receive equivalent advice, described as coming from a prognostic tool or another professional.

This research will provide greater understanding of the factors affecting the quality of MDT prognostic estimates and will provide an evidence-base to improve clinician training.

8 Assessment and Management of Risk

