4.3 Analysis of the primary objective

In order to assess the level to which participants incorporate the advice into their final estimates of the probability of survival, the WOA is calculated for each participant for each vignette(s). This is done by comparing their final estimate against the initial estimate and the advice provided. The final

estimate of probability of surviving two weeks can be represented as a weighted combination of the participant's initial estimate and the advice received, with the weights being proportional to the extent of the shift towards (away from) the advice. WOA will be defined as $= |f - i|/|a - i|$, where 'i', 'f', and 'a' stand for initial, final, and advice, respectively.

If a participant decides to adhere completely to his or her initial estimate (100% discounting of the advice), the weight of the advice will be 0. If the participant decides to shift completely to the advice then the weight of advice will be 1.0 (0% discounting). Intermediate weights indicate that positive weights were assigned to the initial estimate and the advice (partial discounting).

We will then use multilevel regression analysis accounting for multiple vignettes completed by each participant, to compare the means of the WOA scores for the two arms, the algorithm arm and the clinicians' arm.

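### Protocol 16.1 gives a detectable-difference range of 0.085 to 0.22 whose two ends do not share one basis, and it leaves the unit of the SD undefined

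*Protocol*

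**What the plan says.** Protocol 16.1 sizes the study by the precision of the difference in mean WOA between the algorithm-label and clinician-label groups, "with a confidence interval (CI) of 95" per cent. Citing a similar study, it states that "we expect the standard deviation (SD) to be between 0.3 and 0.4". It then says "This will give a width of the CI between 0.17 and 0.31, depending on the sample size and the SD", and Table 1 gives widths for N from 50 to 300 under the column header "Expected SD for mean diff in WOA". The next step turns these widths into a claim about detection: 100 to 200 respondents are said to be enough to find a significant difference if the true mean difference exceeds 0.085 to 0.22.

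Later in the same section the protocol notes that "The online survey consists of five vignettes". It defends that number only as a balance of generalisability and burden. SAP 4.3 calculates one WOA per participant and vignette and says "We will then use multilevel regression analysis accounting for multiple vignettes completed by each participant" to compare the two arms. Neither document gives an intraclass correlation (ICC) for WOAs from the same participant.

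**The concern.** A detectable-difference range should come from one rule applied at the best and worst corners of the planned design. Here the two ends look as though they come from different rules. A reader who takes 0.085 as a difference the study can reliably find would be misled, because a true difference of that size would be missed about half the time even in the most favourable planned case. A reader who takes 0.22 as the matching worst case cannot tell what it represents. Section 16.1 is the only sample-size justification in the two documents, and Protocol 12.3.2 refers to it for the lower recruitment limit.

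The second issue is the SD. The table uses one value per participant, the analysis uses up to five, and the text does not say which of the two quantities the SD of 0.3 to 0.4 describes.

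**Working it through.** **Inputs.** From Protocol 16.1: 95% confidence (z = 1.96), SD σ = 0.3 or 0.4, total N = 100 to 200. The allocation ratio is not stated; 1:1 is assumed, and reproducing the table supports it.

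**Step 1: reproduce Table 1.** Standard error SE = σ × √(4/N); full width = 2 × 1.96 × SE.

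- N=200, σ=0.3: 2 × 1.96 × 0.3 × √(4/200) = 0.166 (printed 0.17)
- N=100, σ=0.4: 2 × 1.96 × 0.4 × √(4/100) = 0.314 (printed 0.31)

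All 12 cells agree to two decimals. Reading N as per arm fails (0.12 at N=200, σ=0.3), and so does a t quantile (0.34 against the printed 0.33 at N=50, σ=0.3).

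**Step 2: put the detection claim on each candidate basis.** The half-width, 1.96 × SE, is the smallest observed difference that would be significant. The 80%-power difference is (1.96 + 0.842) × SE.

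| N | σ | Full width | Half-width | 80%-power difference |
|---|---|---|---|---|
| 200 | 0.3 | 0.166 | 0.083 | 0.119 |
| 200 | 0.4 | 0.222 | 0.111 | 0.158 |
| 100 | 0.3 | 0.235 | 0.118 | 0.168 |
| 100 | 0.4 | 0.314 | 0.157 | 0.224 |

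From the best corner (N=200, σ=0.3) to the worst (N=100, σ=0.4), the range is:

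- full widths: 0.17 to 0.31
- half-widths: 0.08 to 0.16
- 80%-power differences: 0.12 to 0.22

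None of these is 0.085 to 0.22.

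**Step 3: where the two ends could come from.** The lower end is 0.17/2 = 0.085, a half-width taken from the rounded table entry. The upper end, 0.22, matches three different quantities:

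- the full width at N=200, σ=0.4 (0.222)
- the half-width at N=50, σ=0.4 (0.222), which lies outside the planned N
- the 80%-power difference at N=100, σ=0.4 (0.224)

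The protocol does not say which is meant.

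**Step 4: power at the stated lower end.** Power ≈ Φ(difference/SE − 1.96). At N=200, σ=0.3, SE = 0.0424, so Φ(0.085/0.0424 − 1.96) = 0.52. For a true difference of 0.085 the other corners give 0.32 (N=200, σ=0.4), 0.29 (N=100, σ=0.3) and 0.18 (N=100, σ=0.4).

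**Step 5: the unit of σ.** With m = 5 WOAs per participant and per-WOA SD σ, the variance of a participant's mean is σ²(1 + 4 ICC)/5. Every width and detectable difference is then multiplied by √((1 + 4 ICC)/5). The documents give no ICC, so the whole range is shown as an assumption:

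| ICC | Factor | Full width, N=200, σ=0.3 | Full width, N=100, σ=0.4 |
|---|---|---|---|
| 0 | 0.447 | 0.074 | 0.140 |
| 0.3 | 0.663 | 0.110 | 0.208 |
| 0.5 | 0.775 | 0.129 | 0.243 |
| 0.7 | 0.872 | 0.145 | 0.273 |
| 1 | 1.000 | 0.166 | 0.314 |

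If σ is already the SD of the five-vignette mean, the factor is 1 and Table 1 is unchanged. Either way both ends of the detection range scale together, so the mismatch in Steps 2 and 3 does not depend on this choice.

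**The case against.** The best defence of the detection sentence is that the study is planned on precision. N was not derived from a power calculation, SAP section 4 calls the analysis mainly descriptive, and the sentence is only a gloss on the table. That stands as far as N is concerned. It is also true that 0.22 may be a deliberate 80%-power figure for the worst corner, so it should not be called an error in itself. What remains is that 0.085 is not an 80%-power figure for the best corner, so the two ends cannot be read as one range.

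A reader might go further and infer that the widths of 0.17 to 0.31 misstate the design's precision because five WOAs per participant enter the model. The documents do not support this unconditionally. With five complete WOAs each, the multilevel comparison of arms is equivalent to comparing participant means, so Table 1 is correct if σ is the SD of such a mean. Protocol 7.5 describes a series of experiments and details only the one in which "judges were asked to estimate the weight of a person in a photograph". That suggests one judgement per judge, but section 16.1 does not say which experiment supplied the SD, or in what unit. The table header does not settle the matter: read literally it names the SD of a mean difference, whereas the formula treats σ as the SD of individual values.

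**Conclusion.** The stated detectable range is wrong as written. If half-widths were meant, the upper end should be about 0.16, and 0.22 overstates it by about 40% (0.22/0.157 = 1.40). If 80% power was meant, the lower end should be about 0.12, and 0.085 understates it by about 29% (0.085/0.119 = 0.71). This rests only on the protocol's own N, SD and confidence level, with 1:1 allocation and the normal approximation that reproduces Table 1. It holds whichever unit σ has.

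On the SD, what is shown is a missing definition, with no error in the widths. A reader might infer that the sample is too small. It is not shown to be: in the calculation above the factor never exceeds 1, so under the per-WOA reading Table 1 is an upper bound. Two limits apply to any gain from five vignettes. WOA is undefined when the advice equals the initial estimate, so some participants will contribute fewer than five values. Variation of the label effect between vignettes is also left out of the factor.

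**What to change.** In Protocol 16.1, restate the detection sentence for N = 100 to 200 and SD 0.3 to 0.4 on one basis:

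- half-widths of about 0.08 to 0.16, labelled as the smallest observed difference that would reach significance, with about 50% power for a true difference of that size; or
- differences detectable with 80% power, about 0.12 to 0.22.

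Then state whether 0.3 to 0.4 is the SD of a single WOA or of a participant's mean over five vignettes, and correct the column header to match. If it is the mean, keep Table 1. If it is a single WOA, say that Table 1 is conservative and multiply it, and the detection range, by √((1 + 4 ICC)/5). Declare the ICC as an assumption, show it over a range, and note that undefined WOAs reduce the number of values per participant.

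The cost is a reworded paragraph and at most one recalculated table. N, data collection and the SAP model stay as they are. If the protocol can no longer be amended, the same clarification can go into the SAP or the report.
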